9.6. Data management

The processes for database management differ by country. Generally, the data are stored at the database level and analysed locally. High data quality standards will be maintained, and processes and procedures utilized to repeatedly ensure that the data are as clean and accurate as possible when presented for analysis. SAS Software or R language will be utilized for access to the raw data, to manage the analytic datasets and to conduct data analysis. If the study is conducted by a third party, the datasets and analytic programs will be stored according to the vendor's procedures.

This study will follow the relevant chapters of the European Network of Centres for Pharmacoepidemiology and Pharmacovigilance (ENCePP) and the International Council for Harmonization of Technical Requirements for Pharmaceuticals for Human Use guidelines for data management.

9.7. Data analysis

9.7.1. General considerations

A stand-alone statistical analysis plan (SAP) will be developed to describe the definitions of variables for exposures, outcomes, covariates, and subgroups of interest. The SAP will describe in detail the statistical analyses and include a full set of table shells. The SAP will be developed after final protocol approval and before data extraction.

The analyses will be conducted using the statistical software SAS Version 9.4 or above, or equivalent software.

Given the study objectives the analyses will be descriptive, with no intent for hypothesis generating or testing between exposure categories. Incidences in rivaroxaban and SOC exposure categories will be compared only in an exploratory sense and no confirmatory statistical tests will be performed. All analyses will be conducted separately by country and data source. Besides, combined analyses of aggregated data across data sources will be provided, as applicable.

Categorical variables will be presented as counts (n), and proportions (%), with 95% CI where relevant. Continuous variables will be presented as means with standard deviation and as medians with interquartile range, where appropriate.

Due to data protection regulations, and to avoid identification of individual patients, data cells with small numbers of patients (e.g., <5) may not be reported in the data sources. For the same reason, minimum and maximum values for individual variables may not be reported. The data will be presented in a format that complies with these regulations and prevents patient identification.

The planned analyses are summarized below.

9.7.2. Patient characteristics

The impact of inclusion and exclusion criteria on the number of patients in the study population will be described in an attrition diagram or table.

The study population will be described according to the descriptive variables mentioned in [Section 9.3.2.1.1](#).

For each exposure category (rivaroxaban and SOC), analyses of patient characteristics will be described, with stratification on the status of exposure, i.e., initiators versus switchers.

Patient characteristics will also be described over time during the study period to identify potential time trends (secondary objective).

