9.2.2. Study time frame

9.2.2.1. Index date and follow-up

The index date will be the day of initiation of any anticoagulation therapy (rivaroxaban oral suspension or SOC). Patients will be assigned to two exposure categories, rivaroxaban or SOC, according to their actual use of the respective anticoagulation therapy. They may contribute time at risk to more than one exposure category if they switch from one to the other. More specifically, patients will be allowed to switch multiple times between SOC and rivaroxaban and contribute time accordingly to both exposure categories, as long as the same anticoagulant treatment period is continuing.

Patients will be followed from the index date to the earliest of the following censoring criteria:

- End of the anticoagulation treatment period, i.e., discontinuation of all study drugs (rivaroxaban and SOC),
- Death,
- Disenrollment/de-registering/emigration or last available data,

- End of the study period.

Moreover, patients will be followed until the first occurrence of each safety/effectiveness outcome event, with time at risk defined separately for each outcome analysis.

If patients have another initiation of anticoagulant therapy (SOC or rivaroxaban) for a VTE diagnosis before the age of two years, i.e., another qualifying anticoagulant treatment period for a recurrent VTE observed during the inclusion period for which they fulfil all inclusion and exclusion criteria (including a 6-month washout period), they will be allowed to enter the study cohort again, with a new index date.

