9.2.3. Selection criteria

9.2.3.1. Inclusion criteria

Participants are eligible to be included in the study only if all of the following criteria apply:

- Evidence of initiation of an anticoagulant therapy (index drug), either rivaroxaban oral suspension or other anticoagulation therapies (heparins, VKAs, other DOACs). Initiation will be defined as a first record of any anticoagulation therapy (rivaroxaban or SOC) without any anticoagulation therapy in the previous 6 months, or since date of birth for children less than 6 months (see codes for anticoagulant drugs in [Annex 3](#)).
- Evidence of a prior VTE diagnosis (index VTE), defined as the presence of at least one primary/main or secondary diagnosis code for VTE recorded in inpatient setting in the previous 30 days (see preliminary list for VTE codes in [Annex 3](#)).
- Age less than two years on index date.
- Baseline period for availability of patient data history in the data source. A minimal baseline period of six months before index date for children aged between six months and two years, and a baseline period since birth for children less than six months of age will be required.

According to its indication, rivaroxaban oral suspension should be used after at least five days of initial parenteral anticoagulation treatment. In order to describe the actual clinical practice in real world settings, there will no requirement on this initial parenteral anticoagulation treatment to include patients in the study population, so patients will be identified independently of this. In theory, all patients receiving rivaroxaban should be switchers. In practice, they may appear as initiating directly with rivaroxaban: the observed initial anticoagulant therapy might be different from the actually received initial therapy, if patients have switched drug during hospital stay and if inpatient drug data is not captured. Depending on availability of inpatient drug data in each data source, the observed initiation of the anticoagulant therapy will be identified either in outpatient or in inpatient setting, as shown in [Figure 2](#) below (see [Section 9.4](#)).

SOC for treatment of VTE in children usually include UFH, LMWH and VKA and may vary across countries. With other DOACs receiving indication for VTE in paediatrics, SOC may also evolve over time.

Figure 2 Visualization of patient journey

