9.3.2. Outcomes

9.3.2.1. Primary outcomes

9.3.2.1.1. Patient characteristics

The following patient characteristics, including risk factors for VTE will be considered:

- Demographic characteristics of patients: age, sex; bodyweight at index date and gestational age, if available
- Characteristics of index VTE, if available (depending on the granularity of codes):
 - Type of location of VTE
 - Central venous catheter related thrombosis
 - Symptomatic versus asymptomatic VTE
- Co-morbidities reported in the previous six months before index date, or since date of birth for children less than six months:
 - Major organ disease (cardiac, gastrointestinal, renal, neurological)
 - Malignancy (active cancer, haematological cancer, solid tumour)
 - Thrombophilia (congenital or acquired), including antithrombin, protein C or Protein S deficiency, factor V Leiden or prothrombin mutation
 - Major surgery or trauma
 - Major infectious disease
 - Major congenital venous anomaly
 - Use of central venous catheter
 - Morbid obesity
 - Hypertension
- Prior treatments reported in the previous six months before index date (or since date of birth for children less than six months): all drugs by third or fourth ATC level
- Comedication during follow-up: all drugs by third or fourth ATC level, and subgroup of all drugs that can increase the risk of bleeding, such as non-steroidal anti-inflammatory drugs, antiplatelets and aspirin
- Health resource utilization in the previous six months before index date (or since date of birth for children less than six months), e.g., marker of health status of the patients, including

- Outpatient visits
- Hospital admissions
- Length of hospital stay
- Admission to intensive care unit
- Duration of oral, nasogastric/gastric feeding before index date (identified via procedure codes), if available

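### Rivaroxaban switchers are described as of SOC start, because baseline characteristics are anchored at the first anticoagulant but tabulated by exposure category

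*Protocol*

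**What the plan says.** Protocol section 9.2.2.1 sets one anchor: "The index date will be the day of initiation of any anticoagulation therapy (rivaroxaban oral suspension or SOC". A new index date arises only on re-entry for another qualifying treatment period: "including a 6-month washout period), they will be allowed to enter the study cohort again, with a new index date". A switch within a treatment period does not create one.

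Section 9.3.2.1.1 ties the baseline variables to that anchor:
- "Demographic characteristics of patients: age, sex; bodyweight at index date and gestational age, if available"
- "Co-morbidities reported in the previous six months before index date, or since date of birth for children less than six months"
- "Prior treatments reported in the previous six months before index date", or since birth in the youngest
- health resource use over the same lookback.

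Comedication is taken over follow-up ("Comedication during follow-up: all drugs by third or fourth ATC level, and subgroup of all drugs that can increase the risk of bleeding").

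Section 9.7.2 then reports by exposure category: "For each exposure category (rivaroxaban and SOC), analyses of patient characteristics will be described, with stratification on the status of exposure, i.e., initiators versus switchers". On who the switchers are, section 9.2.3.1 says: "In theory, all patients receiving rivaroxaban should be switchers". It adds that in practice some will appear to start directly on rivaroxaban. Section 9.9 explains that this happens where inpatient drugs are not captured, namely SNDS and Sweden.

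**The concern.** The first primary objective is to describe the patients who use rivaroxaban or SOC. A table by exposure category invites the reader to take the rivaroxaban column as the child's state when rivaroxaban began. That is true for initiators. For observed switchers the column stops at SOC start, so initiators and switchers are set side by side with windows that end at different points relative to rivaroxaban.

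Surgery, infection, a new malignancy or intensive care arising between SOC start and rivaroxaban start would not appear. Weight, on which section 7.2 says dose and frequency depend, would be the weight at SOC start. Part of any initiator-switcher difference could then come from where the window closes and not from the children themselves.

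**Working it through.** **1. Where each window ends**

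| Variable (9.3.2.1.1) | Rivaroxaban initiator | Observed switcher from SOC |
|---|---|---|
| Age, bodyweight | rivaroxaban start | SOC start |
| Co-morbidities, prior treatments, resource use | six months (or since birth) to rivaroxaban start | six months (or since birth) to SOC start |
| Comedication | follow-up | follow-up, which runs across both drugs |

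No section sets a second baseline at the switch. Section 9.2.3.1 also requires that no anticoagulant was recorded in the previous six months, or since birth in the youngest. The prior-treatment window is the same, so a switcher's prior treatments contain no anticoagulant by construction, although the child came to rivaroxaban from one.

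**2. The same pathway in different sources (9.9, Table 4)**

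Take a child who starts heparin in hospital and changes to rivaroxaban before discharge. In Denmark and SIDIAP, with inpatient drugs captured, this is a switcher anchored at heparin start. In SNDS and Sweden the child appears as an initiator anchored at the first outpatient rivaroxaban record. Section 9.7.8 plans combined tables of patient characteristics across these sources.

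**3. Reproducing the expected rivaroxaban counts (Table 6)**

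Mean market share = (10 + 32 + 38 + 42 + 50 + 30)/6 = 33.67%.

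| Source | Average children with VTE | × 0.3367 | Table 6 |
|---|---|---|---|
| Denmark | 52 | 17.5 | 18 |
| SNDS | 650 | 218.8 | 219 |
| SIDIAP | 45 | 15.2 | 15 |
| Sweden | 98 | 33.0 | 33 |
| Overall | 846 | 284.8 | 285 |

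The counts reproduce.

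**4. Reach**

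Sources expected to show inpatient SOC: 18 + 15 = 33, and 33/285 = 11.6%. SNDS and Sweden: 219 + 33 = 252, and 252/285 = 88.4%. In the latter, only a child with an outpatient SOC record before rivaroxaban is seen as a switcher. The protocol does not give that share f, so it is assumed here. Affected users = 33 + 252f.

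| f (assumed) | Affected | Share of 285 |
|---|---|---|
| 0% | 33 | 12% |
| 25% | 96 | 34% |
| 50% | 159 | 56% |
| 75% | 222 | 78% |
| 100% | 285 | 100% |

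**5. How much of the lookback is lost**

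Take six months as 183 days. For a switch on day d, the part of the 183 days before rivaroxaban that lies outside the window is d/183. Day 5 is the minimum parenteral lead-in in section 7.2. The later days are assumptions.

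- d = 5: 5/183 = 3%
- d = 30: 30/183 = 16%
- d = 60: 60/183 = 33%
- d = 90: 90/183 = 49%

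For children under six months the window runs from birth, so 183 days is the wrong denominator and the lost share can be larger. As an assumed illustration, with index at age 10 days and switch at age 40 days, (40 − 10)/40 = 75% of the child's history before rivaroxaban lies outside the window.

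**The case against.** The strongest reply has four parts.

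- **Much of the interval is recorded elsewhere.** The SOC agent, its duration, the switch and the sequence of agents are drug-utilization outcomes (9.3.2.1.2, 9.7.3), and a hospitalised bleed on SOC is counted as an SOC outcome (9.7.4). This stands. A reader might infer that the plan misses everything between the two drugs, or that the switcher table describes the SOC period. Neither is right: the baseline variables describe time up to SOC start, and the gap is in the characteristics tables only.
- **Reach is limited.** The statement that all rivaroxaban users are switchers is qualified in the same paragraph, and 88% of expected users are in sources where in-hospital switchers appear as initiators. This stands as a limit on size. It also creates the mixed anchors in the combined tables.
- **Comedication may already be split.** A reader might infer that a bleeding-risk drug taken only during SOC will be listed under rivaroxaban. Section 9.3.1 assigns follow-up time to the respective exposure category, so counting comedication within each category's time is an equally natural reading. The text is ambiguous, and misattribution is not established.
- **Definitions belong to the SAP.** Table shells and operational definitions do. The anchor does not, because the protocol writes the index date into the variables and defines that date. Stratifying initiators from switchers separates the groups but leaves the window where it is.

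It is also fair that sex, gestational age, type of index VTE and inherited thrombophilia do not depend on the anchor, and that bodyweight is collected only where available.

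**Conclusion.** The point holds for the time-varying characteristics of observed switchers. Their rivaroxaban column shows them as of SOC start, with no prior anticoagulant possible, and the combined tables mix two anchors for one clinical pathway.

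Reach runs from about 33 of 285 expected rivaroxaban users (12%) up to all of them. The lower figure assumes that inpatient drugs are captured in Denmark and SIDIAP and that rivaroxaban users there are in fact switchers. The upper figure assumes that every user in SNDS and Sweden has an outpatient SOC record first. The documents do not say where in this range the study will fall.

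For each affected child the loss is slight if the switch comes near day 5 and grows with later switches. The documents give no distribution of switch times. Incidence rates and the as-treated exposure split are unaffected. This is a worthwhile, inexpensive improvement to a descriptive primary objective, not a flaw that undermines the study.

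**What to change.** In sections 9.3.2.1.1 and 9.7.2:

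- For the tables by exposure category, measure age, weight (if available), co-morbidities, prior treatments including the prior anticoagulant, and resource use at the first day in that category. This is the index date for initiators and the switch date for switchers.
- Keep the index-date table for the overall cohort.
- State that comedication is counted within that category's time at risk.

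The cost is a second run of the same code at another anchor date and some extra table columns. The downside is a few more cells near the suppression limits in section 9.7.8 (fewer than five in the Nordic countries, six in Spain, ten in France). This would be felt mainly in Denmark and SIDIAP, where 18 and 15 rivaroxaban users are expected before any split.

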9.7.3. Drug utilization patterns

Drug utilization patterns will be described according to the variables mentioned in [Section 9.3.2.1.2](#).

Exposure duration will be classified into two categories: ≤ 3 months and > 3 months.

A Sankey diagram or equivalent will be used to describe at the patient-level the sequence over time of successive anticoagulant agents/classes.

Drug utilization patterns will also be described over time during the study period to identify potential time trends (secondary objective).

9.7.4. Safety and effectiveness outcomes

Analyses of outcomes will be conducted according to anticoagulation therapy received: rivaroxaban and SOC (including heparins, VKAs, and other DOACs).

Time at risk will consider the exposure of interest (rivaroxaban or SOC) according to the as-treated assumption. For each outcome, the first occurrence for that outcome during time at risk will be identified.

The primary analysis of major bleeding will be based on the outcome definition considering all bleedings at critical sites (or requiring transfusion or resulting in death). A secondary analysis will be based on an analysis per bleeding site if numbers permit.

For each exposure category:

- A crude incidence rate with corresponding 95% CI will be estimated for each outcome.
- The cumulative incidence with 95% CI of each outcome will be estimated at regular time intervals (e.g., at 3, 6, 9 and 12 months).
- Event-free survival of each outcome will be presented graphically with the Kaplan-Meier method.

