Rivaroxaban is the first centrally approved oral anticoagulant product in the European Union (EU) for treatment of secondary prevention of VTE in children. Besides, this orally administered alternative requires less monitoring than existing SOC. Rivaroxaban should be initiated following at least 5 days of initial anticoagulation treatment with parenteral heparins, with dose and frequency of administration based on body weight. In children weighting less than 30 kg, rivaroxaban oral suspension is the only available formulation.

In the pivotal Phase III EINSTEIN Junior study, in the rivaroxaban group, during the main treatment period, a total of four (1.2%; 4/335) children had recurrent VTE, which occurred during heparinization in two children, during tablet treatment in one child, and during suspension treatment in one child. In the comparator group, a total of five (3.0%; 5/165) children had recurrent VTE, resulting in a hazard ratio of 0.40 (95% CI 0.11 – 1.41). All four recurrent VTEs in the rivaroxaban group occurred in the 184 children aged 12 to <18 years (6).

Like for the other anticoagulants, bleeding is an important identified risk for rivaroxaban. In the paediatric population, the safety evaluation of rivaroxaban was mainly based on the pivotal Phase III EINSTEIN Junior study(6). Among 491 included children (329 rivaroxaban, 162 comparator), the incidence of the principal safety outcome during the main treatment period (major bleeding + clinically relevant non-major [CRNM] bleeding) was numerically higher in the rivaroxaban group (10 children, 3%; all CRNM bleeding) compared to the comparator group (three children, 1.9%; two major bleeding, one CRNM bleeding). In the youngest children aged less than two years, there were only 53 patients included (21 and 9 [0.5 to <2 years] and 15 and 8 [<0.5 year], in rivaroxaban and comparator groups, respectively), with two patients (5.6%) in the rivaroxaban group and one patient (5.9%) in the comparator group having a CRNM bleeding. Furthermore, the coagulation system in neonates and infants aged <6 months is different from older children and adults, and extrapolation from adults is less straightforward than for elderly children (1).

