9.1. Study design

This will be an observational, retrospective, descriptive, multi-national cohort study of children initiating anticoagulation therapy. The study will be conducted using secondary data derived from multiple data sources including electronic health records and administrative health insurance claims data in four European countries (France, Sweden, Denmark, Spain).

The study cohort will include all children aged under two years and initiating anticoagulant therapy following a VTE diagnosis. The inclusion period will be from the market launch date of rivaroxaban oral suspension in each country until end of 2026, with follow-up until end of 2027. Patients will be followed up from the anticoagulation therapy initiation (index date), until occurrence of bleeding (major bleeding, and CRNM bleeding as co-primary outcomes) or recurrent symptomatic VTE (as secondary outcome) – with time at risk specific to each outcome, discontinuation of all study drugs, death, exit or last available data from the data source, or end of study period, whichever occurs first. Two exposure categories will be defined, one for rivaroxaban and one for SOC, using an as-treated exposure definition. Patients will contribute time to both exposure categories if they switch from SOC to rivaroxaban or vice versa. As long as the anticoagulant treatment period is continuing, patients will be allowed to switch multiple times between SOC and rivaroxaban and contribute time accordingly to both exposure categories.

[figure not shown]
If patients have another initiation of anticoagulant therapy for a VTE diagnosis before the age of two years, and for which they fulfil all inclusion and exclusion criteria (including a 6-month washout period), they will be allowed to enter the study cohort again with a new index date.

22195; XAPAEDUS; v 2.1, 16 NOV 2022;

Page 17 of 59

based on template version 9

An overview of the study design is presented in [Figure 1](#).

DOAC = direct oral anticoagulant; SOC = standard of care; VKA = vitamin K antagonist; VTE = venous thromboembolism

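### Outcome rates are compared by drug in use without aligning on time since treatment start; where a heparin lead-in is observed, this can tilt the crude contrast towards rivaroxaban, probably modestly

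*Protocol*

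**What the plan says.** Section 9.2.2.1 sets a single index date, the first observed anticoagulant of either category, and adds that "patients will be followed until the first occurrence of each safety/effectiveness outcome event", with time at risk defined outcome by outcome. Section 9.1 adds: "Patients will contribute time to both exposure categories if they switch from SOC to rivaroxaban or vice versa". Section 9.7.4 then fixes the attribution: "Time at risk will consider the exposure of interest (rivaroxaban or SOC) according to the as-treated assumption". For each category it plans a crude incidence rate, cumulative incidence at points such as 3, 6, 9 and 12 months, and a Kaplan-Meier curve. It sets out no strata for time since index and no time origin or delayed entry for a child who switches.

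The protocol expects a heparin phase of at least five days before rivaroxaban, and 9.2.3.1 draws the consequence: "In theory, all patients receiving rivaroxaban should be switchers". Patient characteristics will be shown "with stratification on the status of exposure, i.e., initiators versus switchers" (9.7.2); no such split is planned for outcomes. On use of the results, 9.7.1 says: "Incidences in rivaroxaban and SOC exposure categories will be compared only in an exploratory sense".

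**The concern.** Taken together, these rules give the two categories different windows of treatment time. When a lead-in is recorded, SOC holds the first days of treatment of children who later receive rivaroxaban, with any bleed or recurrence in those days. A child with such an event has left follow-up for that outcome and adds no rivaroxaban time to it. Rivaroxaban time from observed switchers is thus later time, in children selected for having had no event so far.

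If the hazard is constant, nothing is lost. If it is higher soon after the VTE, the crude SOC rate carries more of the high-risk period, and rivaroxaban looks better even when the drugs are equal. The incidence of bleeding by therapy is a primary objective and the reason for the study, and section 9.9 does not mention this source of bias.

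**Working it through.** **1. The plan's own figures.** SNDS, average estimate (Table 6): 650 children. The mean of the six yearly market shares is (10 + 32 + 38 + 42 + 50 + 30)/6 = 33.7%, and 650 × 0.337 = 219 rivaroxaban users, as stated. 219 × 5.6% = 12.3 bleedings, stated as 12. The SOC remainder is 650 − 219 = 431 children and 37 − 12 = 25 bleedings.

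**2. Model with no drug effect.** Assumptions, none given in the protocol: each child is treated for 90 days; the hazard is k for days 0–30 and 1 afterwards, in both categories; a share f of the 219 rivaroxaban children has an observed SOC lead-in of L days (L ≤ 30). Events are rare, so expected events are proportional to cumulative hazard, and loss of children with an earlier event is ignored.

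- Rivaroxaban time: 219 × (90 − fL)
- Rivaroxaban events ∝ 219 × (30k + 60 − fLk)
- SOC time: 431 × 90 + 219 × fL
- SOC events ∝ 431 × (30k + 60) + 219 × fLk

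Example, k = 3, L = 14, f = 1:
- Rivaroxaban: 219 × 108 / (219 × 76) = 23,652/16,644 = 1.421
- SOC: (431 × 150 + 219 × 42)/(38,790 + 3,066) = 73,848/41,856 = 1.764
- Crude rate ratio: 1.421/1.764 = 0.81, although the drugs are identical

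| Observed lead-in | k = 2 | k = 3 | k = 5 |
|---|---|---|---|
| none seen (f = 0) | 1.00 | 1.00 | 1.00 |
| 5 days, all children | 0.96 | 0.93 | 0.90 |
| 14 days, a quarter | 0.97 | 0.95 | 0.93 |
| 14 days, half | 0.94 | 0.91 | 0.87 |
| 14 days, all | 0.88 | 0.81 | 0.73 |

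With k = 1 every entry is 1.00.

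**3. Does standardising remove it?** In the example, rivaroxaban time is 219 × 16 = 3,504 child-days within days 0–30 and 219 × 60 = 13,140 after, that is 21.05% and 78.95%. The SOC hazards weighted this way give 0.2105 × 3 + 0.7895 × 1 = 1.421, equal to the rivaroxaban rate, so the ratio returns to 1.00.

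**4. Does the planned sensitivity analysis remove it?** Section 9.7.6.1 keeps only the first agent episode and adds 30 days. For a child going from heparin to rivaroxaban, this discards the rivaroxaban time and assigns the first 30 days after the switch to SOC. The lead-in stays in SOC. It answers a question about overlapping exposure, not this one.

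**5. Can the lead-in be seen where outcomes are reported?** Sections 9.5.2, 9.7.8 and 9.9 expect outcome analysis to be feasible only in SNDS. Section 9.9 says that inpatient drugs are not captured there or in Sweden, so a child switched in hospital appears as a rivaroxaban initiator. It also says that, at the first outpatient prescription, some children may still be on the parenteral drug. The effect in SNDS therefore comes from that last group only, and the protocol gives no count of it. Denmark and SIDIAP can record inpatient drugs, but Table 4 puts their outcome counts below the disclosure threshold.

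**The case against.** The strongest reply is that the lead-in is largely invisible in the one source expected to report outcomes. This stands: for children switched in hospital, rivaroxaban time starts at the index date, and the shift is nil if no lead-in is seen.

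Second, the study is descriptive, and a 5-day lead-in seen in every child moves the ratio only to 0.96–0.90. Twelve events have an exact Poisson 95% interval of about 0.52 to 1.75 times the estimate, so such a shift would be lost in the noise. This also stands and limits the weight of the point. It does not remove it, because the bias has a known direction if risk is front-loaded, and the protocol says the incidences will be compared.

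Third, the SAP could set the time origin after a switch. That is fair for the curves. The crude rate per category, however, is fixed in the protocol.

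A reader might also infer three stronger things that the documents do not support:
- *That rivaroxaban receives only event-free time.* The time is conditional on no event before the switch; Table 6 expects 12 bleedings in it.
- *That heparin events are charged to the wrong drug.* Heparin person-time goes to SOC with its events. The problem is confounding by time since treatment start, plus selection of children without an earlier event.
- *That the pivotal trial shows the size.* Section 7.2 reports four recurrences in the rivaroxaban group, "which occurred during heparinization in two children, during tablet treatment in one child, and during suspension treatment in one child". Moving the two heparin-phase events would take 4/335 (1.2%) to 2/335 (0.6%). But the same section places all four at ages 12 to under 18, and the outcome is secondary and marked below threshold even in SNDS in Table 4. It shows that lead-in events occur, no more. For bleeding, the protocol gives no event timing.

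**Conclusion.** The point holds as a cheap improvement. Where a lead-in is observed, the common index date, as-treated attribution and stop at first event put early treatment time into SOC and admit switchers to rivaroxaban time only while outcome-free. Nothing in 9.7.4 or 9.7.6.1 aligns the categories on time since start.

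The direction favours rivaroxaban if risk is highest early. The size is unknown and probably modest: of the order of 0.97 to 0.90 in the milder scenarios, 0.88 to 0.73 only if every child has two weeks of observed lead-in, and zero if none is seen or the hazard is constant. All these ratios rest on assumed values of treatment length, early hazard and share of observed lead-ins. They do not show that the study's results will be materially biased.

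**What to change.** In 9.7.4:

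1. For Kaplan-Meier and cumulative incidence, use days since the first observed anticoagulant as the time scale in both categories, with delayed entry at the switch.
2. Beside the crude SOC rate, report one SOC rate standardised to the rivaroxaban person-time distribution by time since index, in two bands (for example 0–30 and over 30 days), and use it for the exploratory comparison. Do not publish band cells below the disclosure limit. Three published bands would not work: 25 SOC bleedings over two co-primary outcomes and three bands average about 4 per cell, against suppression below ten in France.
3. Extend the initiator/switcher split of 9.7.2 to outcomes where disclosure limits allow, and add this limitation to 9.9.

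The cost is a little more programming on data already extracted, a slightly less precise SOC rate, and some suppressed cells. With about 12 rivaroxaban bleedings expected in SNDS, the split in item 3 will often be suppressed; items 1 and 2 do not depend on it.
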